	3. Participants with epilepsy.4. Participants who have undergone nerve block (occipital or other) in the	
	head or neck, or treatment with onabotulinum toxin A (Botox) to the head	
	and/or neck in the prior four months.	
	5. Current participation in any other clinical interventional study	
	Participants without basic cognitive and motor skills required for operating a smartphone.	
	7. Pregnant or breastfeeding females	
	8. Participants who have previous experience with the device	
	9. Participants with arm circumference below 7.9 inches (20 cm)	
Study Design	A prospective, single arm, open label trial.	
	The study will be conducted in two phases:	

Revision #: 1.0

Page: 6 of 20

	Phase I - Run-in: Eligible participants will use a smartphone headache diary application for 28 days. Participants who report at least 22 entries (70%) AND a constant and unremitting headache will be included in the treatment phase. The C-SSRS will be administered at the screening visit and a "since last visit" form which will be administered at each subsequent in-clinic study visit to assess possible suicidal ideation and behavior. The C-SSRS will be scored by the investigator or Study Coordinator who has C-SSRS certification. The survey will be scored immediately after taken by participant. If reports of suicidal ideation with intent to act (endorse item 4 or 5), reports of actual, aborted, or interrupted suicide attempts, or reports of behavior preparatory for an attempt are identified, the investigator" will refer the subject for further examination. Phase II - Treatment phase: Participants who meet the run-in requirements will receive an active Nerivio device. Participants will be instructed to use the device within 60 minutes of awakening with a headache or upon increasing headache severityduring a period of 4 week. A treatment session is of 45 minutes The participants will use the app to record pain intensity levels at baseline and 2-hours post-treatment, and to record the presence/absence of associated	
Qualifying NDHP attack	A qualifying NDPH attack is defined as a headache that: 1. is at an intensity above their baseline pain 2. is present upon awakening	
Primary endpoint	Pain relief at 2 hours post-treatment: The proportion of participants achieving pain relief at 2 hours post-treatment in the test treatment, with no use of rescue/abortive medication (Pain relief defined as a reduction from severe to moderate, mild or none, moderate to mild or none, or mild to none)	

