REN is a novel treatment option which has successfully been shown to reduce migraine headaches in the adult population (Yarnitsky et al, 2020). There is now data to support its use in pediatrics and the device was recently FDA approved for use in pediatric migraine patients ages 12 years and older (Hershey et al, 2021). New daily persistent headache is a constant, unremitting headache disorder with clinical symptoms of migraine and/or tension-type headache and is seen in as many as 14% of pediatric and adolescents patients (Strong et al, 2021). Pediatric patients with a diagnosis of new daily persistent headache are typically resistant to standard pharmacologic treatments and often experience systemic side effects related to medications; thus, REN offers the potential for an exciting new treatment option for patients with refractory headache disorders.

3. Identification and description of the device information

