5.1.1. Inclusion criteria

- Participants age 12-17 years old at the time of informed consent, inclusive.
- Participants have at least a 6-month history of headaches that meet the diagnostic criteria for New Daily Persistent Headache (NDPH)
- Participants who are on stable dosing of prophylaxis agents for at least three months.
- Participants have personal access to a smartphone (24/7)
- Participants must be able and willing to comply with the protocol
- Parents/Guardians must be able and willing to provide written informed consent
- Participants must be able and willing to provide informed assent

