6.4. Statistical analysis

6.4.1. General considerations

Statistical analyses will be performed using SAS® v9.4 or higher (SAS Institute, Cary NC, USA).

Baseline demographic and other baseline characteristics, together with safety analyses will be performed on all participants who underwent the treatment phase. Baseline values are defined as the last valid value prior to treatment.

Where confidence limits are appropriate, a two-sided 95% confidence interval will be constructed.

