6.4.4. Efficacy analysis

The efficacy endpoints will be assessed on evaluable treatments of qualifying attacks. The first use of the device is considered a training treatment and will not be included in the efficacy analyses. The first treatment of a qualifying attack after the training treatment is considered a test treatment and will be used for all efficacy assessments. If this treatment is not evaluable (i.e., no pain data at 2 hours post-treatment), a subsequent treatment of a qualifying attack with evaluable data will be considered the test treatment.

Use of rescue medication before the 2-hours assessment will be considered a treatment failure for the 2-hours endpoints, and before the 24 hours assessment for the sustained 24-hours endpoints. The percentage of participants achieving each of the efficacy outcomes will be presented in a tabular form along with two-sided 95% exact confidence intervals.

For the associated symptoms outcomes, the observed response proportions and corresponding 95% exact confidence intervals for each associated symptom will be provided. All patients with baseline and 2 hours values will be included in the analyses. A response in each associated symptom (nausea, vomiting, photophobia, phonophobia) is defined as change from presence of a specific associated symptom at baseline to absence of the same associated symptom at 2 hours post-treatment.

In addition, logistic regression models will be used to assess the efficacy. Baseline value and site will serve as covariates.

The first secondary endpoint (pain relief at 2 hours) may also be evaluated in attacks with aura and attacks without aura separately.

7. Data management

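### As written, the associated-symptom analysis keeps participants without the symptom in the denominator, so the reported percentage is prevalence times disappearance rather than disappearance

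*Combined protocol and SAP*

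**What the plan says.** Section 5.3.2 lists the disappearance of nausea, photophobia and phonophobia at 2 hours as the second secondary endpoint and gives no denominator. The denominator comes from section 6.4.4, in adjacent sentences:

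- Who is analysed: "All patients with baseline and 2 hours values will be included in the analyses".
- What counts as a response: a "change from presence of a specific associated symptom at baseline to absence of the same associated symptom" at 2 hours.

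The result for each symptom is the observed proportion with a 95% exact confidence interval. The same section has a rescue rule: "Use of rescue medication before the 2-hours assessment will be considered a treatment failure for the 2-hours endpoints". It also treats a test treatment as evaluable or not on the 2-hour pain record alone; symptom records play no part in that.

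Section 5.2 (Phase 2) has participants record in the app whether each symptom is present or absent, at baseline and at 2 hours. Section 6.4.1 adds: "Baseline values are defined as the last valid value prior to treatment".

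**The concern.** The inclusion rule and the response definition do not fit together. The first admits everyone with two recorded values; the second can be met only by someone who starts with the symptom. A participant with no nausea at the baseline of the test treatment has a valid baseline value (absent), enters the nausea analysis, and is counted as a non-responder although there was nothing to resolve.

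This is a single-arm trial, so the percentages and their exact intervals are the main planned result for this endpoint. A reader will take them as disappearance rates. Under the literal rule they answer another question: in what share of all analysed participants was the symptom both present and resolved? Two analysts could also report different percentages from the same data, each with a defensible reading of the text.

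There is a second, narrower conflict. A participant who takes rescue medication before 2 hours and has no 2-hour value for the symptom is a failure under the rescue rule but is left out by the inclusion sentence.

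**Working it through.** **1. Does any other section ensure that the symptom is present?**

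| Section | What it requires | Symptom required? |
|---|---|---|
| 5.1.1 Inclusion criteria | NDPH diagnosis with a history of at least 6 months | No |
| Synopsis, qualifying attack | Headache that "is at an intensity above their baseline pain" and is there on waking | No |
| 5.2 Phase 2 | Presence or absence recorded | No; absent is a recordable value |
| 6.3 mITT | Treatment within 60 minutes of onset; a valid post-baseline assessment for the analysis concerned | No |
| 6.4.1 Baseline | Last valid value before treatment | No |

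The background section describes NDPH as having "clinical symptoms of migraine and/or tension-type headache", which gives no reason to assume that every participant has every symptom.

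**2. What the literal rule estimates.** Let N be the participants with both values, m those with the symptom at baseline, and x those in whom it is gone at 2 hours. Then

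x/N = (m/N) × (x/m) = q × d,

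where q is prevalence and d is the disappearance rate. The shortfall is d − qd = d(1 − q), which is zero only when q = 1 (or d = 0).

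**3. Size.** The plan gives no prevalence, no expected disappearance rate and no derivation of the sample size, so there is no figure of its own to reproduce. The values of q and d below are assumptions, and N = 100 is the enrolment ceiling. Intervals are Clopper-Pearson, 95%, with d = 50%.

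| Prevalence q | Literal rule, x/100 | Among those with the symptom, x/m |
|---|---|---|
| 30% | 15/100 = 15% (8.6 to 23.5) | 15/30 = 50% (31.3 to 68.7) |
| 80% | 40/100 = 40% (30.3 to 50.3) | 40/80 = 50% (38.6 to 61.4) |
| 90% | 45/100 = 45% (35.0 to 55.3) | 45/90 = 50% (39.3 to 60.7) |
| 100% | 50/100 = 50% (39.8 to 60.2) | the same |

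The gap d(1 − q) for other assumed values, in percentage points:

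| | d = 30% | d = 50% | d = 70% |
|---|---|---|---|
| q = 30% | 21 | 35 | 49 |
| q = 80% | 6 | 10 | 14 |
| q = 90% | 3 | 5 | 7 |

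**4. The interval read as an interval for d.** With x following a binomial (N, 0.5q) distribution, the probability that the literal exact interval contains d = 50% is:

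| Prevalence q | N = 100 | N = 50 |
|---|---|---|
| 60% | 2.1% | 21.8% |
| 80% | 53.8% | 76.3% |
| 90% | 86.5% | 92.1% |
| 100% | 96.5% | 96.7% |

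This is the same gap seen another way, not separate evidence. It shows how far the printed interval could mislead someone who takes it at face value.

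**5. The rescue conflict.** Suppose 80 participants have the symptom, 40 respond, and 8 were rescued and have no 2-hour symptom value (all assumed). Leaving out the 8 gives 40/72 = 55.6% (43.4 to 67.3). Counting them as failures gives 40/80 = 50% (38.6 to 61.4). This error favours the device, the opposite direction to the first.

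**6. The logistic model.** Section 6.4.4 names the baseline value as a covariate. Under the literal denominator, absence at baseline predicts non-response perfectly (quasi-complete separation). Under the restricted denominator that covariate is constant.

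**The case against.** The best answer is that the inclusion sentence is only a completer rule. It names one condition, having both values, which is how such rules are usually written. Section 6.3 has a general rule of the same kind, dropping subjects without a valid post-baseline assessment from the analysis concerned. The response definition starts from presence, and the word disappearance presupposes something to disappear. On that reading the plan is unclear, not wrong. This may well be what was intended, but the text does not say so, and an analyst who applies the sentence as it stands gets the wrong denominator. The completer reading also leaves the rescue conflict in place.

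The rescue conflict is fairly called narrow. Pain and symptoms are recorded in the same app at the same times, so it affects only participants who were rescued, recorded 2-hour pain and lack the 2-hour value for that symptom. Nothing in the documents suggests a large group, and the 8 of 80 above is purely illustrative.

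It is also true that every magnitude rests on assumed inputs, and that the 49-point extreme needs both low prevalence and high disappearance. The endpoint is one of four secondary endpoints and carries no test or threshold. Those points limit the importance of the finding; they do not remove it.

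**Conclusion.** The concern holds. Section 6.4.4 states a rule which, followed as written, produces prevalence times disappearance instead of the disappearance rate that section 5.3.2 names. No other section corrects it.

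The size cannot be determined from the documents. Under the assumed ranges the understatement is 6 to 49 points for prevalence between 30% and 80% and disappearance between 30% and 70%, 3 to 7 points at 90% prevalence, and nil at 100%.

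The change should be made, but the trial does not stand or fall on it: no success criterion uses these percentages, the literal denominator errs in the conservative direction, and the intended rate can be recovered from the data. The rescue conflict is smaller in scope but runs in the favourable direction. Confidence is medium, because the intended reading is uncertain.

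**What to change.** Replace the inclusion sentence in section 6.4.4 with wording such as:

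> For each symptom, the analysis includes participants with that symptom present at the baseline of the test treatment who either have a 2-hour value for that symptom or used rescue medication before the 2-hour assessment; the latter count as failures whether or not a 2-hour value was recorded.

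In the results table, show for each symptom how many had it at baseline and how many were analysed. If a logistic model is fitted for a symptom, leave out that symptom's own baseline as a covariate.

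Two small items should be tidied at the same time. The general exclusion in section 6.3 needs a cross-reference so that it does not remove the rescued participants again. Section 6.4.4 lists vomiting, which section 5.2 does not have the app record and section 5.3.2 does not name; without a baseline record, no denominator can be formed for it.

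The cost is one sentence, a table column and these small edits, with no new data. The intervals widen because the denominators are smaller. With N = 100 and 50% disappearance (assumed), the width goes from 14.9 to 37.4 points at 30% prevalence, and from about 20 to 22.8 points at 80%. That is the actual precision available for the named endpoint.

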7.2.	Records and data retention	17

Revision #: 1.0

Page: 4 of 20

8.	Device accountability	17
9.	Informed consent process	17
10.	Adverse events	17
10.1.	Characteristics of AEs	18
10.2.	Reporting of AEs and SAEs	19
10.3.	Anticipated device-related AEs	19
11.	Patient confidentiality & data protection	19
12.	Guidelines and applicable documents	19
13.	Reference	20

Revision #: 1.0 Page: 5 of 20

1. Synopsis

Title	A prospective, single arm, open label study of the safety and efficacy of Nerivio™ for the acute treatment of New Daily Headache Persistence (NDHP) in adolescents	
Principal Investigator	[name]	
	Director, Pediatric Headache Program	
	Associate Professor of Pediatrics and Child Neurology, George Washington	
	School of Medicine and Health Sciences	
	Children's National Hospital, Washington, DC	
Investigational	Nerivio [™] is an FDA-authorized Remote Electrical Neuromodulation (REN) device for the acute treatment of migraine with or without aura in patients	
Device	12 years old or above. The device delivers transcutaneous electrical	
	stimulation to the upper arm to induce conditioned pain modulation (CPM) that	
	activates a descending endogenous analgesic mechanism.	
Objectives	To evaluate the safety and efficacy of Nerivio™ in the acute treatment of New	
	Daily Headache Persistence (NDHP) in adolescents (12 to 17 years of age).	
Participant	Adolescents 12-17 years old meeting the International Headache Society	
Population	criteria for New Daily Persistent Headache (NDPH)	
Sample size	Up to 100 participants	
Inclusion Criteria	1. Participants age 12-17 years old at the time of informed consent, inclusive.	
	2. Participants have at least a 6-month history of headaches that meet the diagnostic criteria for New Daily Persistent Headache (NDPH)	
	3. Participants who are on stable dosing of prophylaxis agents for at least three months.	
	4. Participants have personal access to a smartphone (24/7)	
	5. Participants must be able and willing to comply with the protocol	
	6. Parents/Guardians must be able and willing to provide written informed consent	
	7. Participants must be able and willing to provide informed assent	
Exclusion Criteria	Participants with an implanted electrical and/or neurostimulator device (e.g. cardiac pacemaker, cochlear implant).	
	2. Participants with congestive heart failure (CHF), severe cardiac or	
	cerebrovascular disease.	

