
Revision #: 1.0

Page: 7 of 20

Within-patient consistency

The repeatability of headache reduction, as described in the primary endpoint definition, in subsequent treated attacks. Thus, this endpoint measures the % of patient responding to the primary endpoint in at least 50% of their treated attacks

Disappearance of associated symptoms at 2 hours post-treatment

Disappearance of nausea, photophobia and phonophobia at 2 hours post-treatment

Functional disability at 2 hours post-treatment

The proportion of participants achieving improvement of at least one grade in functional disability in the test treatment at 2 hours post-treatment with no use of rescue medication

Improve of quality of life

Reduction in average headache disability as measured by PedsMIDAS before and at 1 month after initiation of treatment with REN.

Revision #: 1.0 Page: 8 of 20

Exploratory endpoints	 Reduction in average headache intensity at 1 month after initiation of treatment with REN Reduction in perceived stress as it relates to headache, and adverse reactions experienced as measured by HIT-6.
Safety endpoints	 The safety of Nerivio The incidence of adverse events in general and by seriousness, severity and association to the device. Treatment tolerability The percent of subjects who fail to complete the study because of adverse events
Datasets	 Intent to treat analysis set (ITT) The ITT analysis set includes all participants undergoing the treatment phase. Modified intent to treat analysis set (mITT) The mITT analysis set includes all participants undergoing the treatment phase who treat a test treatment within 60 minutes of attack onset.
Data Analysis	The ITT analysis set will be used for the primary endpoints of safety and tolerability assessments. Safety assessments will include spontaneously reported adverse events. The mITT analysis set will be used for the efficacy assessments.

Revision #: 1.0

Page: 9 of 20

2. Background

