During the training, participants will also be informed on the key elements which are critical for the successful conduct of the study:

Revision #: 1.0 Page: 13 of 20

- Treatments of headache with Nerivio[™] should be performed within 60 minutes of awakening with a headache or upon increasing headache severity and always within one hour of symptoms onset. Treatments of mild headaches are accepted.
- Avoid taking rescue medications within two hours post-treatment (2 hours from start of treatment), if possible.

Revision #: 1.0

Page: 14 of 20

• The treatment should be performed for 45 minutes.

In addition, participants will complete study questionnaires, as required.

Phase 2 – Treatment phase: Participants will be instructed to use the device within 60 minutes of awakening with a headache or upon increasing headache severity during a period of 4 week. Participants will be instructed to use the device with the intensity level identified during the device training visit (with a range of ±5 units) and make sure the stimulation is perceptible but not painful. Participants will be instructed to avoid taking rescue medications within 2 hours post-treatment. If medications are used, participants will be instructed to record in the app when and which medication was taken. The participants will use the app to record pain intensity levels (none, mild, moderate, or severe) at baseline and 2 hours post-treatment, and to record the presence/absence of associated symptoms (nausea, photophobia, phonophobia) at baseline and 2 hours post-treatment.

Participants who do not achieve satisfactory relief at 2 hours post-treatment may treat again with the Nerivio[™] device or may treat with usual care at that time or any time thereafter if the headache does not resolve.

Third (final) visit – End of study: Participants will return to the clinic following the end of the 4-week treatment phase, at which time they will return the device and complete the required questionnaires

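### The logistic regression in section 6.4.4 has no treatment term, reference value or named estimand, so it adds no efficacy information to the exact-CI proportions; the one-test-treatment rule beside it conflicts with the consistency endpoint

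*Combined protocol and SAP*

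**What the plan says.** The Synopsis describes the design as "A prospective, single arm, open label trial". Neither the hypothesis (section 4.2), the sample size (section 6.2) nor the efficacy analysis (section 6.4.4) gives a performance goal or reference response rate.

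Section 6.4.4 sets out the main efficacy analysis: "The percentage of participants achieving each of the efficacy outcomes will be presented in a tabular form along with two-sided 95% exact confidence intervals". It then adds a second one: "In addition, logistic regression models will be used to assess the efficacy. Baseline value and site will serve as covariates". It does not say which outcome is modelled, which quantity is reported or what would be tested. Section 6.4.1 defines baseline as the last valid value before treatment.

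On which treatments count, section 6.4.4 says: "The first treatment of a qualifying attack after the training treatment is considered a test treatment and will be used for all efficacy assessments". Treatment continues on awakening with a headache or "upon increasing headache severity during a period of 4 week" (section 5.2), so repeated treatments are expected. The first secondary endpoint (Synopsis and section 5.3.2) is within-patient consistency: "this endpoint measures the % of patient responding to the primary endpoint in at least 50% of their treated attacks".

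On sites, the available text names only the principal investigator's hospital (Synopsis). The number of sites is not stated.

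**The concern.** A logistic model said to assess efficacy should contain a quantity that speaks to efficacy: a treatment contrast, or a response probability set against a stated value. This one has neither. What it will print is a baseline coefficient, perhaps a site coefficient, and an intercept. If these are reported under an efficacy label, a reader has nothing in the plan to say that they are not evidence of benefit.

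The one-treatment rule raises a second problem. Read literally, it leaves the consistency endpoint without data, because that endpoint is a fraction of each participant's treated attacks. It also keeps every treatment after the test treatment out of the 2-hour analyses. No method is given for the correlation between treatments in the same participant.

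**Working it through.** **Plan's own figure.** The only design figure is 100 participants (section 6.2; up to 100 in section 5.1). No power, assumed response, reference rate or dropout is given, so it cannot be reproduced. The points below are mainly structural.

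**1. What the stated model contains.** With one arm and one test treatment per participant, the model is

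logit(p) = a + b × baseline + c × site.

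- b describes how response varies with pre-treatment value.
- c describes how response varies between sites.
- a is the log-odds of response at the reference values of the covariates. The default test of a = 0 is a test of 50% response at those values, a null that the plan never chose.

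None of these is a device effect.

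**2. What it adds to the tabulated proportion.** For a maximum-likelihood logistic fit with an intercept, the score equation for a is Σ(y − p̂) = 0. The mean fitted probability therefore equals the observed proportion. A simulated data set of 100 participants confirmed this: observed 0.600, mean fitted 0.600. The overall rate is already tabulated with its exact interval, for example at n = 100:

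| Responders | Exact 95% CI |
|---|---|
| 50 | 39.8-60.2% |
| 60 | 49.7-69.7% |
| 70 | 60.0-78.8% |

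**3. Site.** If there is only one site, the columns (intercept, baseline, site) number 3 but have rank 2, so c is not estimable.

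**4. The two rules on treatments, side by side.** Section 6.4.4 says that the single treatment "is considered a test treatment and will be used for all efficacy assessments". Section 5.3.2 classifies a participant by response in at least 50% of treated attacks. With one treatment per participant that fraction can only be 0 or 1, and the endpoint collapses into the primary one. Both statements cannot hold.

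**5. What the later treatments could add (illustration).** Inputs: n = 100 (documents, as the maximum); 95% two-sided (section 6.4.1); response 50%, m treatments per participant and intraclass correlation ICC (all assumed, none in the documents). With equal m:

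D = [1 + (m − 1) × ICC] / m; effective N = 100 / D; half-width = 1.96 × √(0.25 × D / 100).

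One treatment: D = 1, half-width = 1.96 × √0.0025 = 9.8 points. The exact interval for 50/100, 39.8-60.2%, has half-width 10.2.

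| m | ICC | D | Effective N | Half-width (points) |
|---|---|---|---|---|
| 5 | 0.3 | 2.2/5 = 0.44 | 227 | 6.5 |
| 5 | 0.7 | 3.8/5 = 0.76 | 132 | 8.5 |
| 5 | 0.9 | 4.6/5 = 0.92 | 109 | 9.4 |
| 10 | 0.3 | 3.7/10 = 0.37 | 270 | 6.0 |
| 10 | 0.7 | 7.3/10 = 0.73 | 137 | 8.4 |
| 10 | 0.9 | 9.1/10 = 0.91 | 110 | 9.3 |

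The gain depends mainly on ICC and nearly vanishes when a participant's treatments mostly agree.

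**The case against.** Several objections have force.

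- **The regression is an addition.** The main analysis is the table of proportions with exact intervals, and no test or decision rule is tied to any coefficient. This stands. A reader might infer that the efficacy analysis as a whole is unsound; the documents do not support that.
- **Repeated treatments are not ignored.** A reader of section 6.4.4 alone might conclude that they go unused. The consistency endpoint relies on them, and PedsMIDAS and average headache intensity at 1 month are not single-treatment outcomes either. What stands is narrower: the two rules conflict, and later treatments are left out of the 2-hour analyses and the regression.
- **The study is not stated to be single-centre.** A reader might infer it from the one affiliation named, but the documents do not say so. The site covariate is unexplained, not shown to be redundant. If it is constant, it drops out and changes no other estimate.
- **The replacement has no treatment term either.** True. In a single-arm study a response probability is the only efficacy quantity available, and the stated model could yield one too. The replacement is better because it names its estimand, uses data not already in the table and allows for clustering.
- **The intervals in the illustration are not like for like.** True. The primary is a participant-level proportion for one treatment; the alternative averages over treatments. The narrower interval is not a sharper estimate of the primary endpoint.
- **Clustering does not deal with frequent treaters.** True. Robust standard errors allow for correlation, but they do not remove bias when the number of treatments depends on response, for instance if non-responders stop using the device.

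**Conclusion.** The point holds in a limited form. As specified, the regression describes how response varies with baseline value and possibly with site; it adds no efficacy information to the exact-CI proportions. The one-test-treatment rule in section 6.4.4 contradicts the consistency endpoint and must be reconciled with it. The primary analysis is unaffected, so this is a correction that should be made and not a fault that invalidates the study.

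The structural conclusions need no assumed numbers; non-estimability of site is conditional on there being one site. The precision gain is an illustration only. Under the stated assumptions the half-width is 13% to 39% smaller at ICC 0.3-0.7 (1 − √0.76 and 1 − √0.37) and about 4-5% smaller at ICC 0.9 (1 − √0.92 and 1 − √0.91). These ratios do not depend on n, but they assume equal numbers of treatments per participant. No part of this supplies a comparator.

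**What to change.** Keep the single test-treatment proportion with its exact interval as primary. Limit the one-treatment rule to the endpoints defined on the test treatment, and replace the regression sentence with text such as:

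> Within-patient consistency uses all evaluable treatments of qualifying attacks. As a supportive analysis, 2-hour pain relief over all evaluable treatments of qualifying attacks after the training treatment will be analysed by a GEE logistic model with independence working correlation and robust standard errors clustered on participant. The marginal response probability will be reported with a 95% CI, together with an estimate giving each participant equal weight. Any coefficient for pre-treatment pain will be reported as response by severity, not as efficacy. Site will be included only if there is more than one.

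The participant-weighted estimate is a necessary part of the change, because the number of treatments may depend on response. Section 5.2 allows a further treatment when relief is unsatisfactory, so the text should also say how repeat treatments of the same headache are counted in this analysis.

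The cost is a wording change and one extra supportive analysis. Section 5.2 already has participants record pain in the app at baseline and 2 hours, so no new data are needed. The downside is an attack-level estimand that differs from the primary one and must be labelled as such.
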